**Exclusion Criteria:**

- Allergy to benzoyl peroxide or chlorhexidine
- <18 years of age
- Female Gender
- Previous history of shoulder infections
- Antibiotics taken within one month of research visit
- Immunocompromised state
- Active cancer
- Diabetes
- Skin lesions or abrasions over the deltopectoral interval
- Topical corticosteroid treatment to either shoulder or systemic corticosteroid treatment within 2 weeks of research visit
- Topical benzoyl peroxide treatment to either shoulder within 2 weeks of research visit
- Blue light therapy treatment to either shoulder within 2 weeks of research visit
- Prior incision over the deltopectoral interval of either shoulder
- Contraindication to blue light treatment

[figure not shown]
**Demographics Collected:** An intake form will be distributed to each subject consented to participate in the study. Demographics to be obtained include: age, height, weight, profession, race, medical comorbidities, surgical history, and showering habits.

At the final research visit, subjects will be asked questions regarding their experience with the treatment they were assigned to on a Likert Scale. The subjects will also be asked regarding their satisfaction with the treatment they received, as well as a set of “would you rather” hypothetical questions regarding their preference of pre-operative experience.

#### **Randomized Groups:**

- N=20
  - 5% Topical Benzoyl Peroxide Gel + 2% Chlorhexidine Gluconate with 70% Isopropyl Alcohol. Contralateral shoulder serving as control (2% Chlorhexidine Gluconate with 70% Isopropyl Alcohol only)
- N=20
  - Blue Light Therapy + 2% Chlorhexidine Gluconate with 70% Isopropyl Alcohol. Contralateral shoulder serving as control (2% Chlorhexidine Gluconate with 70% Isopropyl Alcohol only)
- N=20
  - 5% Topical Benzoyl Peroxide Gel + Blue Light Therapy + 2% Chlorhexidine Gluconate with 70% Isopropyl Alcohol. Contralateral shoulder serving as control (2% Chlorhexidine Gluconate with 70% Isopropyl Alcohol only)
- In addition to randomizing subjects to one of the 3 above groups, subjects will be randomized to have either their right or left arm as the “treatment” arm with the contralateral serving as control. Within each group of 20 subjects, 10 will be randomized to having the right arm as the “treatment” arm and 10 will be randomized to having the left arm as the “treatment” arm.
  - Randomization will be performed using concealed envelopes to be picked at random once a subject is consented for participation in the study.

- The research coordinator consenting subjects and coordinating the blue light treatment will not be blinded given their involvement. The remainder of the research team will be blinded to both treatment arm as well as which side (left or right) served as the control.
- **Figure 1** below details the 3 separate groups that subjects could be randomized to. Each of the 3 groups will contain 20 subjects. Within each of the 3 groups, subjects will be randomized to having either the right or the left arm being the treatment arm. The treatment arm means that arm will receive either 5% topical benzoyl peroxide, blue light therapy, or both. The contralateral shoulder will be the control for each subject.

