In recent years, topical methods of eradicating or reducing the skin burden of *C. Acnes* have been investigated, including chlorhexidine swabs and topical benzoyl peroxide (BPO) as oral antibiotics including doxycycline have not proven effective. Topical BPO has been shown in several studies to be superior to chlorhexidine in reducing bacterial load using swab cultures of the epidermis and deep sebaceous glands. However, several drawbacks of topical BPO have been described including bleaching of clothing, requirement for serial application leading to poor compliance, potential for irritant and allergic contact dermatitis, and inconsistency in eradicating *C. Acnes* in some reports. In addition, there is concern that topical treatments may not penetrate into the superficial dermal layers to eradicate bacteria colonizing 1 mm beneath the skin surface, where the sebaceous glands reside.

Blue light therapy, with wavelength 405nm-470 nanometers (nm), is an Food & Drug Administration (FDA) approved modality that has previously been described in the dermatology literature as a highly effective antimicrobial agent against *C. Acnes*, among other bacteria, in mild to moderate inflammatory acne patients. The benefit of blue light therapy is that a single treatment can kill 99.9% of *C. Acnes*. The anti-microbial mechanism of action involves absorption by endogenous porphyrins which induce generation of reactive oxygen species leading to cell death and DNA cleavage. In contrast to topical antimicrobials, blue light therapy penetrates to 1.2-1.5 mm beneath the skin surface to eliminate bacteria residing in the sebaceous glands. Blue light demonstrates bactericidal effects at doses as low as 5 J/cm^2, while higher doses (>100 J/cm^2) are necessary to injure human tissues. Wavelengths of 405-415 nm with a radiant exposure of 54 - 75 J/cm^2 have been demonstrated to exert the greatest antimicrobial effects against *C. Acnes*. Variables that affect radiant exposure include: power of the blue light device (W), desired surface area to be treated (cm^2), time duration of treatment (s). Devices with lower irradiances (W/cm^2) require treatment for a longer time duration (s) to

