#### **E: Research Design and Methods**

**Study Design:** Single-Blinded (investigators performing analysis), randomized controlled trial

**Study Participants/Human Subjects:** 60 volunteers

**Power Analysis:** Power analysis calculations were performed using G\*Power (Universität Kiel, Germany). With an  $\alpha$  of 0.05 and 90% power to detect a 50% difference in positive culture rates as previously described, it was determined that 51 total patients needed to be enrolled. For the purposes of the present study, assuming a 15% attrition rate, it was determined that 20 subjects per group, 60 subjects total, were necessary.

**Inclusion Criteria:** Healthy Male Volunteers at least 18 years of age

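### Envelopes are picked from an unordered set by an unnamed person, so no described control would reveal a re-draw; numbered envelopes opened in order would cost almost nothing

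*Combined protocol and SAP*

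**What the plan says.** All of this is in section E, mostly under Randomized Groups.

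- Mechanism: "Randomization will be performed using concealed envelopes to be picked at random once a subject is consented for participation in the study".
- Fixed totals: "Each of the 3 groups will contain 20 subjects", and by side, "Within each group of 20 subjects, 10 will be randomized to having the right arm as the “treatment” arm and 10 will be randomized" to the left. That makes six cells of 10.
- Blinding: the design is "Single-Blinded (investigators performing analysis), randomized controlled trial". "The research coordinator consenting subjects and coordinating the blue light treatment will not be blinded given their involvement". For everyone else, "The remainder of the research team will be blinded to both treatment arm as well as which side (left or right) served as the control".

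The protocol does not say who prepares, keeps or picks the envelopes. It also leaves open whether they are opaque, sealed or numbered, how the sequence is generated, whether group and side share one envelope, and whether draws are recorded.

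Under Treatment Description and Culture, swabs are taken only after treatment, one set from each shoulder. The contralateral shoulder receives chlorhexidine preparation alone.

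**The concern.** Concealing the contents of an envelope does not fix the order in which envelopes are used. If they are numbered and opened in sequence, a skipped or replaced one leaves a gap. In an unordered set, an envelope that is opened, put back and replaced by another pick leaves none. The returned envelope is used later, so the totals still reconcile.

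The groups also differ in what they ask of subject and staff: five gel applications starting 48 hours before the visit, against one 23-minute session in the blue-light-only group. Section C lists among the drawbacks of the gel a "requirement for serial application leading to poor compliance". This does not show that anyone would re-draw. It does mean that the groups are not equally convenient, and a re-draw made for convenience could be selective.

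At stake are Aims 1 and 2, which compare treatments between different men. Blinded reading of cultures protects the outcome assessment but not the make-up of the groups.

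**Working it through.** **1. The plan's own figures.** None is given for allocation. The group size is reproducible: 51 / (1 − 0.15) = 60, and 60 / 3 = 20. The 51 itself is matched by a chi-square test with effect size w = 0.5, 2 degrees of freedom, alpha 0.05 and 90% power. Both w and the degrees of freedom are my assumptions, because the text says only "of 0.05 and 90% power to detect a 50% difference in positive culture rates as previously described".

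**2. What a re-draw does.** At the start there are 60 envelopes, 20 for each group (a pool of exactly 60 is implied by the fixed totals). The chance of a wanted group is 20/60 = 33.3%. If an unwanted first envelope is held aside while a second is taken and is then returned, the chance becomes 1 − (40/60)(39/59) = 55.9%. With two such re-draws it is 1 − (40/60)(39/59)(38/58) = 71.1%. In both cases all 60 envelopes are eventually used, so the final counts remain 20/20/20 and 10/10.

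**3. Shift in the group difference.** Suppose k exchanges each move a man with positive-culture probability pH from one group to another, in return for a man with probability pL. The difference between the groups moves by 2k(pH − pL)/20.

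- Culture status known in advance (pH = 1, pL = 0): 2/20 = 10 points per exchange, 20 points for two.
- 70% vs 10%, two exchanges: 4 × 0.6/20 = 12 points.
- 60% vs 20%: 4 × 0.4/20 = 8 points.
- 50% vs 30%: 4 × 0.2/20 = 4 points.
- Trait unrelated to culture: 0 points.

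**4. False-positive rate.** I enumerated all outcomes of two binomials with n = 20 and 40% positive in each group, at a two-sided 0.05 level. The plan states neither the 40% nor the sidedness, and names no test, so I used uncorrected chi-square and Fisher.

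With culture status known in advance (upper bound):

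- no exchange: 4.8% (chi-square), 2.4% (Fisher)
- one exchange: 9.8%, 5.7%
- two exchanges: 25.1%, 17.2%

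For true rates from 20% to 50%, two exchanges give 23% to 36% (chi-square) and 15% to 25% (Fisher).

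With two exchanges on a visible trait held by half the men, 40% positive overall, chi-square:

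- unrelated to culture: 4.8%
- 50% vs 30% positive: 5.6%
- 60% vs 20%: 7.9%
- 70% vs 10%: 11.9%

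These let the trait mix vary by chance in each group. If each group starts with exactly ten men of each type, the three related-trait cases give about 5% to 6%.

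**The case against.** The strongest reply is that this is thin reporting rather than a flawed method, and that the harm is hypothetical. Several parts of it stand.

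- A reader might infer that the unblinded coordinator draws the envelopes. The text does not say so: the sentence is passive, and the subject or another person could pick.
- A reader might conclude that re-draws would be undetectable. The protocol describes no control that would reveal them, but it does not exclude sealing or a log.
- The 25% and 17% rates might be read as the effect of two re-draws. They require knowledge of a culture that is read after seven days' incubation, and with no pre-treatment swab nobody at the draw has it.
- The control shoulder, swabbed at the same visit, reflects each man's underlying colonisation. Steering colonised men into one group would tend to show as imbalance there and could be partly adjusted for. Age, weight, race, comorbidities and showering habits are also collected. With 20 men per group the check is imprecise, and no adjusted analysis is specified.
- The predictability of late allocations might be offered as a further reason for the change. In simulation, someone keeping a tally names the next group correctly 42.4% of the time overall and 59.2% over the last 10, against 33.3% by chance. This comes from the fixed totals, not from picking at random, and a numbered list with the same totals is equally predictable. On average only about 1.5 of the 60 allocations are certain. As the pick follows consent, a guess can affect only whom to approach and when.

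The core is not answered. The plan does state a mechanism, an unordered pick, and numbered envelopes opened in order are a better one. A re-draw acts after consent, so drawing after consent does not prevent it.

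**Conclusion.** The concern holds as a weakness in the safeguards, not as evidence of bias. The described procedure has no fixed order, no named custodian and no record. The person who consents subjects is unblinded, and the fixed totals would reconcile even after re-draws. Aims 1 and 2 rest on comparisons between groups of 20 men with no baseline swab, and the control shoulder is only a partial check.

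The documents do not allow the size of any bias to be derived. Two exchanges could raise the false-positive rate to 25% (chi-square) or 17% (Fisher) at most when 40% are positive, if culture status were known. For a trait only partly related to colonisation, the chi-square rate is roughly 5% to 12%. The number of exchanges, the positive rate, the trait's prevalence and strength, and the test are all assumptions. The case for change rests on the very low cost and on the fact that the order of allocation cannot be reconstructed once enrolment is over.

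**What to change.** Replace the pick at random with the following.

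- One computer-generated list of 60 allocations: 3 groups × 2 sides, 10 in each cell.
- Sequentially numbered, opaque, sealed envelopes holding group and side, prepared from that list by an existing team member who takes no part in consent or treatment.
- Envelopes opened strictly in number order, after consent, with subject number, date and time written on the outside before opening.
- A log that accounts for all 60 envelopes.
- A statement in the protocol of who prepares, holds and opens them.

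The cost is a sentence or two of protocol text and about an hour of preparation. Sample size and study procedures do not change. Late allocations remain partly predictable because the totals stay fixed, so that should not be given as a reason for the change.

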**Treatment Description:**

- 5% Topical Benzoyl Peroxide Gel: A pea-sized amount, ~0.5 grams, will be applied to a 10cm strip over the deltopectoral interval beginning the morning 48 hours prior to schedule research visit to obtain cultures. The benzoyl peroxide will be applied on dry skin after a shower. The gel will be applied once in the morning and once in the evening for two consecutive days as well as the morning of the scheduled research visit. Following treatment, both the treatment shoulder and control shoulder will be steriley prepped with 2% chlorhexidine gluconate solution with 70% isopropyl alcohol and allowed to dry for 3 minutes. Following chlorhexidine preparation, a single set of cultures will be obtained from each shoulder.
- Blue Light Therapy: FDA cleared blue light product, Omniluxblue (Globalmed Technologies, Glen Elen, CA), which emits a 415 nm blue light irradiance of 40mW/cm^2 was used. This product has been shown to be safe and effective. The dimensions of the LED light active area is 6 inches x 14 inches, which completely covers the anterior shoulder. To achieve the radiant exposure of 54 J/cm^2 necessary for previously published antimicrobial effects against *C. Acnes*, 23 total minutes of treatment time (1,380 seconds) will be necessary (achieving a total radiant exposure of 55.2 J/cm^2). Following the application of blue light protective eyewear, the blue light therapy device will be centered over the deltopectoral interval according to device standardized use instructions and a 23-minute treatment will be administered to dry skin. As was done in the topical BPO group, following treatment, both the treatment shoulder and control shoulder will be steriley prepped with 2% chlorhexidine gluconate solution with 70% isopropyl alcohol and allowed to dry for 3 minutes. Following chlorhexidine preparation, a single set of cultures will be obtained from each shoulder. Research subjects and research personnel conducting the blue light treatments will be wearing medical grade blue light protective glasses for safety.
- For the subjects randomized to both blue light therapy and 5% topical benzoyl peroxide gel: 5% topical benzoyl peroxide treatment will be performed on dry skin immediately after a shower as described in the above paragraph. Again, five total treatments will be performed prior to research visit. On the day of the research visit, the blue light therapy protocol described above will be performed exactly the same followed by culture obtainment.

**Culture:**

- Each research participant will have skin swab cultures obtained after the completing the assigned treatment. The method described by Scheer et al to obtain the skin swab cultures will be utilized. Specifically, all skin swabs will be taken by rubbing 15 times over a 10 cm deltopectoral interval. Cultures will be sent for both aerobic and anaerobic growth with speciation.
- Our previous protocol detailed that the main laboratory for the University of Wisconsin Hospital & Clinics located at [name] was to be used to run all skin swab culture and speciation for this study. Due to inflexibility in protocols and significant costs, we have elected to utilize the academic microbiology laboratory of [name], MD, PhD. [name] is a full professor, attending faculty in the department of infectious disease and microbiology at the University of Wisconsin School of Medicine

and Public Health. She maintains a research laboratory staffed by several graduate and post-graduate individuals located at both the University of Wisconsin Hospitals & Clinics as well as a second space at the William S. Middleton Memorial Veterans Hospital.

- The culture protocol previously published by Kolakowski et al was used with few exceptions. Following swab collection, the swab culture tips were broken at a breakpoint into to individual 4 mL tubes containing 2 mL of Letheen broth and placed into a biohazard bag. Samples contained in biohazard bags will be placed into a pre-chilled insulated cooler and transported within 4 hours to our microbiology laboratory. In the lab, sample tubes containing swab tips were individually removed from the pre-chilled insulated cooler and vortexed to mix well. Two hundred microliters ( $\mu$ L) of sample were transferred to a 5 mL Falcon tube containing 1.8 mL of 0.05% Tween-80 in water and mixed well (dilution 1). Dilution 2 will be prepared by transferring 200  $\mu$ L of dilution 1 to a 5 mL Falcon tube containing 1.8 mL of 0.05% Tween-80 in water and mixing well. Dilution 3 will be prepared by transferring 200  $\mu$ L of dilution 2 to a 5 mL Falcon tube containing 1.8 mL of 0.05% Tween-80 in water and mixing well. Dilution 4 will be prepared by transferring 200  $\mu$ L of dilution 3 to a 5 mL Falcon tube containing 1.8 mL of 0.05% Tween-80 in water and mixing well.
- Spot plates will be prepared in duplicate by transferring 50  $\mu$ L of the original sample and each dilution (a total of 5 spots for each plate) to a Brucella agar plate. Sample solutions will be allowed to dry on the agar plate and then transferred to an anaerobic environment and allowed to incubate at 37 °C for 7 days. After 7 days of incubation, plates will be checked for growth and spot dilutions that can be read will be counted. Presumptive positive colonies will be subbed to Brucella agar for additional workup (gram stain, catalase test, and indole test). Presumptive positive samples will have a crude PCR lysate made and will be undergo a confirmatory 16s PCR test. We will be obtaining a virulent strain of *C. Acnes* was obtained and how we used that as gold standard methodology.

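### No check that benzoyl peroxide residue on the swab is neutralised, so negative cultures from gel-treated shoulders may not be separable from inhibition in the assay

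*Combined protocol and SAP*

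**What the plan says.** All of this is in section E of the combined protocol and SAP.

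- **Gel (Treatment Description).** "A pea-sized amount, ~0.5 grams, will be applied to a 10cm strip over the deltopectoral interval". It is used "once in the evening for two consecutive days as well as the morning of the scheduled research visit". For the combination arm the count is given: "five total treatments will be performed prior to research visit". On washing: "The benzoyl peroxide will be applied on dry skin after a shower". No wash after the last application is described. Both shoulders then get the chlorhexidine/alcohol prep and 3 minutes of drying.
- **Who gets gel (Randomized Groups).** The treated shoulder in two of the three arms. Blue-light-only shoulders and all contralateral control shoulders get none.
- **Swab and tube (Culture).** The swab is rubbed 15 times over 10 cm of the deltopectoral interval. Then "the swab culture tips were broken at a breakpoint into to individual 4 mL tubes containing 2 mL of Letheen broth", and the tubes are chilled and "transported within 4 hours to our microbiology laboratory".
- **Plating (Culture).** The undiluted sample and four tenfold dilutions are spotted in duplicate, 50 microlitres each. Only presumptive positives go on to PCR.
- **Reference strain (Culture).** "We will be obtaining a virulent strain of" *C. acnes*, described as a gold standard. The sentence is garbled and does not describe an inhibition control.
- **Source of the method (Culture).** A published culture protocol is followed, with a small number of unspecified departures. What the broth is meant to neutralise is not stated.

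**The concern.** The endpoint is whether *C. acnes* grows. That measures skin clearance fairly only if an organism on the swab has the same chance of growing whichever arm it came from. Chlorhexidine residue, if any, is common to every shoulder. Benzoyl peroxide residue, if any, is confined to gel-treated shoulders, because gel is applied "as well as the morning of the scheduled research visit" to the strip that is later swabbed.

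If residue killed or suppressed organisms in the tube or on the undiluted spot, true positives would become negatives in two arms only. The contralateral control shoulder receives no gel, so it can neither reveal nor cancel this. PCR cannot recover such a sample, because it is run only after growth. Both aims compare arms that would then be measured with different sensitivity.

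**Working it through.** **1. The plan's own figure.** The sample size is not in dispute and reproduces. A chi-square test with 3 groups by 2 outcomes, effect size w = 0.5, df = 2, alpha 0.05 and power 90% gives N = 51. Then 51 / 0.85 = 60, or 20 per arm. The documents give no figure for carry-over, so the rest is conditional on stated assumptions.

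**2. How much could reach the tube.** Last application: 0.5 g × 5% = 25 mg. Concentration = 25 mg × fraction carried / 2 mL. The fraction is assumed, because the documents do not give it.

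| Fraction of last dose carried | Undiluted tube | Dilution 1 |
|---|---|---|
| 0.01% | 1.25 micrograms/mL | 0.125 |
| 0.1% | 12.5 | 1.25 |
| 1% | 125 | 12.5 |
| 5% | 625 | 62.5 |

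For shoulders without gel the value is 0. No inhibitory concentration is given, so the table cannot be turned into a share of positives lost.

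**3. Whether the dilution series protects the result.** Two undiluted 50 microlitre spots sample 0.1 / 2 = 5% of the tube. Two dilution 1 spots sample 0.5% of it. With 20 colony-forming units (CFU) in the tube:

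- at least one colony on the undiluted spots: 1 − 0.95^20 = 64%;
- at least one colony on the dilution 1 spots: 1 − 0.995^20 = 10%.

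Low-count samples, which decide positive against negative, depend on the undiluted spots, where any residue is most concentrated. Dilution also cannot reverse killing that has already happened in the tube.

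**4. What a loss would do.** Let f be the share of gel-arm positives lost in the assay, so that the observed rate is the true rate × (1 − f). The plan names no test for comparing two arms. The check uses the exact two-sided Fisher test at 0.05 with 20 per arm. The true rates and f are assumptions.

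| f | Gel reads, if both arms truly 50% | Chance gel falsely looks better | Gel reads, if truly 75% | Chance of showing the advantage of blue light (truly 25%) |
|---|---|---|---|---|
| 0 | 50% | 1.0% | 75% | 83% |
| 10% | 45% | 2.3% | 67.5% | 67% |
| 25% | 37.5% | 6.6% | 56.25% | 40% |
| 50% | 25% | 26.9% | 37.5% | 8% |

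With equal true rates of 30% or 70%, the false-gel chance at f = 25% is 4.2% or 12.9%. With 17 per arm, the last column reads 79%, 62%, 34% and 6%.

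**5. Direction by contrast.**

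- *Aim 1, blue light versus gel:* the bias favours gel.
- *Aim 2, combination versus blue light alone:* only the combination is exposed. If the true rates are equal, the false-gel column applies to a false added benefit.
- *Aim 2, combination versus gel alone:* both arms have the exposure, so there is no built-in difference. Both rates could be pushed toward zero, leaving less room to see what blue light adds.

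**The case against.** The strongest reply is that neither transfer nor inhibition is shown. The documents give no residue on the skin after the prep, no hours between gel and swab, and no fraction lifted. The alcohol/chlorhexidine prep may remove much of the gel. The plan also does not use an arbitrary method. It attributes its culture method to a published protocol, and the reference-list entry for the named source (item 18) is a benzoyl peroxide trial, although the superscript in the Culture section points to item 1. The broth may have been chosen with this residue in mind, and that source may have checked recovery. All of this stands, and it is why the point must be stated as a possibility. It does not close the point, because the plan neither reports such a check nor says what the broth neutralises.

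Four stronger readings are tempting, and the documents do not support them:

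- *Gel is carried into the tube and inhibits growth.* Neither step is measured or stated.
- *The trial could falsely declare blue light the winner.* The bias runs the other way and is conservative for the stated hypothesis.
- *All of Aim 2 would show a false benefit.* This applies only to combination versus blue light alone. Aim 2 is worded around what blue light adds to gel, and that contrast shares the exposure.
- *The dilution series already provides a check.* A reader might compare undiluted with dilution 1 counts, expecting 10:1. Loss in the tube happens before dilution 1 is made, so both counts fall together and the ratio does not move. Only suppression on the undiluted spot could shift it. The comparison also leaves out culture-negative samples, so a normal ratio would reassure falsely.

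**Conclusion.** The concern holds as an unresolved assay risk, not as a demonstrated bias. On the plan as written, a negative culture from a gel-treated shoulder cannot be told apart from inhibition in the tube or on the undiluted spot, and the exposure exists in two of the three arms only.

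The size cannot be derived from the documents. Each 0.1% of the last dose carried over means 12.5 micrograms/mL, with no inhibitory level to compare it with. The Fisher figures show how sensitive the comparison would be to a given loss, not how large the loss is. They rest on assumed true rates, assumed losses and an assumed test. Under them a 25% loss would roughly halve the chance of showing a true 50-point blue-light advantage (83% to 40%). The direction is firmer than the size: any such effect favours gel.

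**What to change.** Before the first swab, run a bench recovery control with the *C. acnes* reference strain the laboratory already plans to obtain.

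1. Spike a low known count into 2 mL Letheen tubes containing study gel at, for example, 0, 0.1%, 1% and 5% of one application (0, 0.5, 5 and 25 mg of gel, or 0, 12.5, 125 and 625 micrograms/mL benzoyl peroxide). Include unspiked blanks. Use replicate tubes: the duplicate undiluted spots sample 5% of a tube, so 20 CFU gives one expected colony.
2. Hold the tubes chilled for 4 hours, then dilute, plate and incubate as in the Culture section.
3. Fix in advance the acceptable recovery relative to gel-free tubes.
4. If recovery meets the limit, say so in the protocol. If not, add a neutraliser to the collection broth for every swab in all arms, after the same bench test shows that it restores recovery and does not itself harm *C. acnes*.

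Do not rely on the undiluted to dilution 1 count ratio in trial samples as the carry-over check.

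The test shows whether inhibition occurs over a range of gel amounts. It does not measure how much gel a real swab lifts, so the limit should apply across the whole range chosen. The cost is a few tubes and plates, a short bench delay and possibly a changed broth. It needs no extra subjects or skin swabs and changes no treatment.
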